10.2 Adverse event recording – general

The collection and reporting of Adverse Events (AEs) will be in accordance with the UK Policy Framework for Health and Social Care Research, the principles of GCP, and the Medicines for Human Use Clinical Trials Regulations 2004 (and its subsequent amendments). Definitions of different types of AEs are listed in Section 10.1 Definitions above. Patients will be questioned about Adverse Events at all follow up appointments. Exacerbations of COPD will not be reported as Adverse Events in this study as they are expected in this patient population and form the basis of the trial design.

The Investigator should document all AEs experienced by the trial participant in the participant's medical notes and assess the severity and causality (relatedness) with reference to Section 4.8 'Undesirable Effects' of the following Summary of Product Characteristics (SPC):

BCG vaccine

Investigators will be provided with a copy of the most recent BCG SmPC at site setup and sites will be responsible for ensuring that this is filed in the Investigator Site File (ISF). Any subsequent updates to the SmPC will be provided by the STABILISE Trial Office and should be implemented immediately by the site and filed in the ISF; the previous versions should be marked as superseded.

All events will be documented in the medical notes from randomisation until the end of 12 month follow up period.

10.3 Adverse event reporting in STABILISE

The following non-serious AEs (and ARs) occurring from the time of trial treatment commencement until end of 12 month follow up should be reported in the relevant CRF but there is no requirement for specific reporting to the trial's unit beyond this routine data collection.

- Localised skin reaction to vaccine
- Fever
- Headache
- Injection-site abscesses
- Local reactions
- Lymphadenitis

The assessment of severity for AEs and ARs that do not meet the criteria for serious will not be collected due to the well understood safety profile of BCG. Assessment of severity of SAEs and SARs will be captured (see section 10.4 below).

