9.5 Follow up visits – One month and three months (mechanistic sub-group only)

If a participant has agreed to take part in the mechanistic sub-group, visits to their local research site will be arranged by the site at one and three months from the date the participant's BCG was administered for those in the intervention arm or from the date of randomisation for those in the control arm. Site staff will take additional blood samples from participants at these visits. During the three-month visit, questionnaires will be completed as for all other patients and DBS test performed. The DBS test will be sent to the main laboratory based at the QE hospital.

Data point to be collected:

- Venepuncture
- DBS
- Exacerbations since baseline
- Hospitalisations
- CAT test

9.6 Three month follow up visit (participants not taking part in the mechanistic sub-group)

Participants will be sent a link via email or SMS text message to access and complete their three month follow up questionnaire at home (paper copies can be posted if requested). This is sent to the participant automatically by the trial EDC system. Participants will also complete a DBS test at home and post the sample to the main laboratory based at the QE hospital. If a participant does not complete the questionnaire online after being sent the link three times on days 2, 3 and 5 from the missed due date, the trial team will send the questionnaire via post (paper) to the participant 7 days from the missed due date. The participant will be asked to complete and return the questionnaire to the trial team at BCTU, in the format it was received. If no response is received/completed after the attempts have been made, this data will be considered missing for this follow up time point.

Data point to be collected:

- DBS
- Exacerbations since baseline
- Hospitalisations
- CAT test

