9.8 Schedule of assessments

Event	Baseline	IGRA test	Vaccine administered ¹	1 month +/-7 days ²	3 months +/- 14 days ²	12 months +/- 1 month ²
Eligibility check	X					
Consent	X					
IGRA test	X	X ³				
Demographics	X					
Medical history (including vaccine history)	x					х
Smoking status	X					Х
Medications	X					Х
Spirometry (FEV1/FVC)	X					
CAT score	X				X	Х
Randomisation	X					
IGRA test results		Х				
Pregnancy test (if applicable)			x			
BCG			X			
Exacerbation rate/symptoms/treatment	x				X	х
DBS (all participants)	X				X	Х
Sputum sample	X				Х	
Throat/nose swab	X				Х	
DBS (exacerbation sampling)					Х	

Table 2: Schedule of Assessments

STABILISE Protocol

Venepuncture	Х		X4	X4	X ⁴
Follow up questionnaire				Х	X
Adverse events				Х	Х

¹ The vaccine, where allocated, should be administered to the participant within 6 weeks of randomisation.

²Follow up dates will be calculated using the date that the treatment was administered on for those allocated to the intervention arm and the date of randomisation for those allocated to the control arm.

³Further test required if result of first test is indeterminate

⁴*Mechanistic subgroup only*

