10. ADVERSE EVENT REPORTING

10.1 Definitions

Table 3: Adverse event reporting definitions

Severity Definitions	Mild Moderate Severe	Awareness of signs or symptoms that do not interfere with the participant's usual activity or are transient and resolved without treatment and with no sequelae. A sign or symptom, which interferes with the participant's usual activity. Incapacity with inability to do work or perform usual activities.
Adverse Event	AE	Any untoward medical occurrence in a participant administered a medicinal product and which does not necessarily have a causal relationship with this intervention. An AE can therefore be any unfavourable and unintended sign (including abnormal laboratory findings), symptom or disease temporally associated with the use of an investigational medicinal product, whether or not related to the investigational medicinal product.
Adverse Reaction	AR	All untoward and unintended responses to an IMP related to any dose administered. An AE judged by either the reporting Investigator or Sponsor as having causal relationship to the IMP qualifies as an AR. The expression reasonable causal relationship means to convey in general that there is evidence or argument to suggest a causal relationship.
Serious Adverse Event	SAE	Any untoward medical occurrence or effect that: Results in death Is life-threatening* Requires hospitalisation or prolongation of existing hospitalisation Results in persistent or significant disability or incapacity Is a congenital anomaly/birth defect Or is otherwise considered medically significant by the Investigator**
Serious Adverse Reaction	SAR	An AR which also meets the definition of a SAE.
Unexpected Adverse Reaction	UAR	An AR, the nature or severity of which is not consistent with the applicable product information (e.g., Investigator Brochure for an unapproved IMP or (compendium of) Summary of Product Characteristics (SPC) for a licensed product).

		When the outcome of an AR is not consistent with the applicable product information the AR should be considered unexpected.
Suspected Unexpected Serious	SUSAR	A SAR that is unexpected i.e., the nature, or severity of
Adverse Reaction		the event is not consistent with the applicable product information. A SUSAR should meet the definition of an AR, UAR and SAR.

* The term life-threatening is defined as diseases or conditions where the likelihood of death is high unless the course of the disease is interrupted.

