14.2.1 Primary estimand

The primary estimand is the rate of moderate to severe acute exacerbations of AECOPD in adults with a primary clinical diagnosis of COPD and will be measured as the rate per person per year. The estimand will follow the principal stratum strategy and those who will be randomised and then receive a positive or indeterminate result in their IGRA test will be excluded from all analyses.

The primary estimand can be summarised as follows:

Population: Adults with a primary clinical diagnosis of COPD and a negative IGRA test, ≥2 AECOPD in the last 12 months, who have not been Immunosuppressed and have not received >20mg prednisolone per day for >14 days in the last 3 months, have not previously experienced of allergic reaction to vaccine and are not pregnant, if they are female.

Treatment Conditions: BCG vaccine compared to no vaccine (see Section 7.1 for details on the intervention)

Outcome: Rate per person per year of moderate to severe acute exacerbations of AECOPD

Time: 12 months after randomisation in the no vaccine group and 12 months after receiving the BCG vaccine in the BCG group

Summary Measure: Adjusted incidence rate ratio and 95% confidence interval

Intercurrent Events and Strategies: The intercurrent events are: positive or indeterminate IGRA test; treatment non-receivers (those who randomised to receive but did not receive the BCG vaccine for any reason); withdraw consent for providing follow up data or lost to follow up; and death. All intercurrent events apart the first one (i.e. tested positive in their IGRA test) will be dealt with using the treatment policy strategy for the primary estimand as we want to evaluate the treatment effect as it would occur in normal practice. The intercurrent event, positive or indeterminate IGRA test will be dealt with using the principal stratum strategy because we are interested in the treatment effect in the principal stratum in which the intercurrent event would not occur.

Other strategies evaluating different estimands will be discussed in further detail in the SAP.

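### CRF reporting of non-serious adverse events starts at a moment the no-vaccine arm never reaches, and the visit data lists omit the adverse events that Table 2 schedules

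*Protocol*

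**What the plan says.** Four parts of the protocol bear on this.

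- **Section 10.3** names six non-serious events: localised skin reaction, fever, headache, injection-site abscess, local reactions and lymphadenitis. Its rule on their window reads: "The following non-serious AEs (and ARs) occurring from the time of trial treatment commencement until end of 12 month follow up should be reported". The CRF in which they are to be reported is not identified.
- **Table 3 (section 10.1)** begins its definition of an adverse event with "Any untoward medical occurrence in a participant administered a medicinal product". Section 14.2.1 gives the treatment conditions as "BCG vaccine compared to no vaccine".
- **Section 10.2** uses a different origin for the source record: "All events will be documented in the medical notes from randomisation until the end of 12 month follow up period". It also states: "Patients will be questioned about Adverse Events at all follow up appointments".
- **Sections 9.5 to 9.8** cover follow-up. Table 2 has a row labelled "Adverse events", marked at 3 and 12 months without the footnote that restricts other entries to the mechanistic sub-group. It is not marked at 1 month. Outside the sub-group, section 9.6 makes the 3-month contact remote: "Participants will be sent a link via email or SMS text message to access and complete their three month follow up questionnaire at home". The data points listed in 9.5 and 9.6 include dried blood spot, exacerbations, hospitalisations and the CAT. Section 9.7 adds history, medication and smoking items. None of the three lists has an adverse-event entry.

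Table 2 footnote 2 sets the follow-up clock at the administration date for the BCG arm and the randomisation date for controls. Section 8.2.1 uses randomisation where no treatment was given.

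**The concern.** The trial is open and has no placebo, so there is no dummy injection to stand in for treatment start in the control arm. A site that follows 10.3 literally has no reporting window to open for a control, or for a participant allocated to BCG who does not receive it. Read with Table 3, such a participant cannot have an adverse event at all.

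This matters little for injection-site reactions, which controls cannot have. It matters for fever, headache and lymphadenitis, which can arise without an injection. A rate of these in vaccinated participants can be interpreted only if the same question is put to both arms over a comparable window.

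The second strand is practical. If the 3-month questionnaire is built from the list in 9.6, nobody asks most participants about these events early on. If the 12-month form is built from 9.7, it does not ask specifically either. Staff working from Table 2 would collect the events; staff working from 9.5 to 9.7 would not. No analysis plan can later recover data that were never collected.

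**Working it through.** **1. Denominator.** Section 14.1 gives 361 per group before loss and 10% loss to follow-up. 361 / 0.90 = 401.1, which rounds up to 402 per group and 804 in total, as stated. The sample size enters this point only as a denominator.

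**2. Who has in-person follow-up before month 12.** Section 17.5 sets the detailed sub-study at 80 participants. Only they have the 1- and 3-month site visits in 9.5.

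- In the sub-group: 80 / 804 = 9.95%.
- Outside it: 804 − 80 = 724, and 724 / 804 = 90.05%.
- In the BCG arm, with the even split given in Appendix A1.2: 402 − 40 = 362, and 362 / 402 = 90.05%.

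**3. Who has a defined start under 10.3.** Vaccinated BCG participants do. The 402 controls and any BCG-arm non-receivers do not. The protocol gives no expected number of non-receivers.

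**4. The provisions side by side.**

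| Contact | Section 10.2 | Table 2 | Data list |
|---|---|---|---|
| 1 month, sub-group | question | not marked | 9.5: no item |
| 3 months, sub-group | question | marked | 9.5: no item |
| 3 months, all others | depends on whether a remote form counts as an appointment | marked | 9.6: no item |
| 12 months | question | marked | 9.7: no item |

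Table 2 and the data lists disagree at both 3 and 12 months. Table 2 and 10.2 disagree at 1 month. Table 7 names a serious adverse event form but no form for non-serious events; it says that it is not exhaustive, so this is only supporting evidence.

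**5. Which events need a control comparison.** Three of the six (localised skin reaction, injection-site abscess, local reactions) have no real counterpart without an injection. The other three (fever, headache, lymphadenitis) do.

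**6. Choice of origin for a repair.** Section 7.1 allows up to 6 weeks between randomisation and vaccination, and BCG-arm follow-up ends 12 months after vaccination. Starting both arms at randomisation would give a vaccinated participant a window up to 6 weeks longer than a control's, or 6 / 52 = 11.5% of a year. All of that extra time would fall before vaccination. The clock in Table 2 footnote 2 gives 12 months in each arm and avoids this.

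**The case against.** The strongest reply is that collection is already scheduled. Table 2 marks adverse events at 3 and 12 months for everyone, 10.2 requires questioning at appointments, and footnote 2 gives controls a clock. Sections 10.2 and 10.3 also govern different records (medical notes and CRF), so two origins are not in themselves a contradiction. All of this stands. A reader might infer that the protocol cannot yield a controlled rate of these events, or that adverse events are missing from every follow-up schedule. The documents support neither.

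A reader might also infer that most participants have no contact before month 12. That is not so: everyone has a 3-month contact, BCG recipients attend an administration visit within 6 weeks of randomisation, and section 11.1 requires events reported by telephone to be documented in the source. Only scheduled in-person follow-up is absent.

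The direction of any bias is not established. Asking only vaccinated participants would exaggerate the difference between arms, while late recall would shrink it. The documents also give no frequency of fever or headache during exacerbations.

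Finally, no comparison of mild reactions is among the trial's outcomes, the protocol relies on the vaccine's well-understood safety profile, and serious events are reported under 10.4 without reference to treatment start. This limits the consequence. It does not reconcile the sections, and form content left to be settled later still has to follow one of two conflicting instructions.

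**Conclusion.** The point holds as an internal inconsistency with a practical consequence. The CRF window in 10.3 is undefined for the 402 controls and for BCG-arm non-receivers, and the Table 3 definition excludes them if read literally. The lists in 9.5 to 9.7 omit what Table 2 schedules and 10.2 requires, and the 1-month sub-group visit is unmarked. The protocol therefore does not secure like-for-like ascertainment of fever, headache and lymphadenitis. For 724 of 804 participants (90%), the only scheduled follow-up before month 12 is a remote questionnaire with no listed adverse-event item.

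The 90% figure measures how many participants rely on that questionnaire; it is not an estimate of lost data. It assumes full recruitment and a sub-group of exactly 80. The conclusion also assumes that sites and form designers may follow 10.3 and 9.5 to 9.7 as written. If the actual forms already carry these items in both arms, what remains is a correction of wording. Serious adverse event reporting and the primary outcome are unaffected.

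**What to change.** - In 10.3, define the CRF reporting start by the clock in Table 2 footnote 2: vaccination date in the BCG arm, and randomisation date for controls and, as in 8.2.1, where no vaccine was given.
- Reword the adverse-event definition in Table 3 so that it covers participants in both arms.
- Add the listed events, each with an onset date, to the 3-month questionnaire and the 12-month form for both arms, with the injection-site items for vaccinated participants only. Add the same entry to the data lists in 9.5, 9.6 and 9.7.
- Reconcile the 1-month column of Table 2 with 10.2.

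The cost is a wording amendment, a few items on existing forms and slightly more data entry. No visit, treatment or sample-size change is needed.

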10.4 Serious Adverse Advents (SAE) reporting in STABILISE

For all SAEs, the PI or delegate must do one of the following:

Record safety reporting-exempt SAEs in the medical notes but **not report** them to the trial's office on an SAE form 10.4.1Serious Adverse Events not requiring reporting to the Trial Office

Error! Reference source not found.Error! Reference source not found.

Report SAEs to the trial office in an expedited manner (within 24 hours of the site research team becoming aware of the event). 10.5SAE Reporting process

10.4.1 Serious Adverse Events not requiring reporting to the Trial Office

At whatever time they occur during an individual's participation, from randomisation, to end of participant follow-up, the following are not considered to be critical to evaluations of the safety of the trial:

• Pre-planned hospitalisation

All events which meet the definition of serious must be recorded in the participant notes, including the causality and severity, throughout the participant's time on trial, including follow-up, but for trial purposes these events do not require reporting on the SAE Form. Such events are "safety reporting exempt".

10.4.2 Admission for AECOPD

The population enrolling in STABILISE are expected to be admitted for COPD, and in this case admission for AECOPD is a study outcome. Duplication of data collection via SAE forms is therefore not planned. 10.5.2Assessment of expectedness of an SAE by the CI

Such events should still be recorded by the trial team in the participant's notes and as a trial outcome.

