10.4.3 Serious Adverse Events requiring expedited reporting to the Trial Office

All SAEs not listed in Sections 10.4.1 and 10.4.2 10.4.1 Error! Reference source not found. must be reported to the Trial Office on a trial specific SAE form within 24 hours of the site research team becoming aware of the event.

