10.5.1 Assessment of causality of an SAE

When completing the SAE form, the PI (or, throughout this section, a medically qualified delegate) will be asked to define the nature of the seriousness and causality (relatedness; see Table 4: Categories of causality) of the event. In defining the causality, the PI must consider if any concomitant events or medications may have contributed to the event and, where this is so, these events or medications should be reported on the SAE form.

As per Table 4: Categories of causality, all events considered to be 'possibly', 'probably', or 'definitely' related to the intervention will be reported by the trial office as 'related'; all events considered at site to be 'unlikely' or 'unrelated' to the intervention will be reported by the trial's office as 'unrelated'. The same categorisation should be used when describing AEs and protocol-exempt SAEs in the source data.

Category	Definition	Causality	
Definitely	There is clear evidence to suggest a causal relationship, and other possible contributing factors can be ruled out.		
Probably	There is evidence to suggest a causal relationship, and the influence of other factors is unlikely.	Related	
Possibly	There is some evidence to suggest a causal relationship. However, the influence of other factors may have contributed to the event (e.g., the participant's clinical condition, other concomitant events or medication)		
Unlikely	There is little evidence to suggest there is a causal relationship. There is another reasonable explanation for the event (e.g., the participant's clinical condition, other concomitant events or medication).	Unrelated	
Not related	There is no evidence of any causal relationship.		

Table 4: Categories of causality

On completion of an SAE Form, the Trial Office will contact the Chief Investigator (CI) or delegate(s) and ask them to access the electronic SAE form and independently* review the causality of the SAE.

An SAE judged by the PI or CI or delegate(s) to have a reasonable causal relationship ("Related" as per Table 4: Categories of causality) with the intervention will be regarded as a related SAE (i.e., SAR). The severity and causality assessment given by the PI will not be downgraded by the CI or delegate(s). If the CI or delegate(s) disagrees with the PI's causality assessment, the opinion of both parties will be documented, and where the event requires further reporting, the opinion will be provided with the report.

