10.6 Reporting SAEs to third parties

The independent Data Monitoring Committee (DMC) may review any SAEs at their meetings.

The Trial Office will report details of all SARs (including SUSARs) to the MHRA, Research Ethics Committee (REC), and UoB Research Governance Team (RGT) annually from the date of the Clinical Trial Authorisation, in the form of a Development Safety Update Report (DSUR). Additionally, the Trial Office will report a minimal data set of all individual events categorised as a fatal or life threatening SUSAR to the MHRA, REC, and RGT within 7 days of being notified. Follow-up information will be provided within an additional 8 days.

All other events categorised as SUSARs will be reported within 15 days of being notified.

Details of all SUSARs and any other safety issue which arises during the course of the trial will be reported to the PIs. A copy of any such correspondence should be filed in the ISF and Trial Master File (TMF).

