11.2 Case Report Form (CRF) completion

The CRFs will include (but will NOT be limited to) the following Forms (see Table 7: Case report forms in STABILISE7).

Form Name	Schedule for submission
Screening CRF	At the point of screening
Decliner's form	At the point of screening and only for those who don't want to take part in the trial but happy to complete the decliner's form
Informed Consent Form	At the point of consent
Initial Visit Baseline CRF	As soon as possible after consent

Table 7: Case report forms in STABILISE

Baseline blood sample details and results CRF	As soon as possible when the blood results are available
Participant contact details CRF	As soon as possible after consent
GP surgery details CRF	As soon as possible after consent
Randomisation CRF	At the point of randomisation
IGRA Test Results	As soon possible after first IGRA result available
IGRA repeat blood sample details and results	As soon as possible after receipt of
Form	indeterminate blood result
Vaccine Administration CRF	At the point of treatment administration
Sub-study blood sample CRF	As close to one, three and twelve months following the treatment administration date for the intervention arm and randomisation for the control arm.
Sub-study blood sample Lab CRF	As soon as blood results are available
Three month follow up questionnaire	As close to the three month follow up time point as possible
Twelve month follow up CRF	As close to the twelve month follow up time point as possible
Withdrawal and change of status CRF	At the point of change of status, withdrawal or death
Serious adverse event reporting form	At the point of being aware of an SAE
Pregnancy Notification Form	At the point of being aware of a pregnancy
Pregnancy Outcome Form	As soon as the pregnancy ends
Sputum sample, Nasopharyngeal (nose and throat) swab and finger-prick receipt patient completion form	To be provided as soon as an exacerbation occurs at home
Exacerbation symptoms and treatment - Participant completion	At the point of exacerbation
Sputum sample receipt, Nose/throat swab, DBS test Lab CRF (lab forms completed by lab staff)	All AECOPD episodes
Adjudication panel diagnosis confirmation	To be completed as soon as the adjudication committee meet every 3 months.
Qualitative sub-study participant consent form	At the point of enrolment into the qualitative sub-study
Qualitative Demographic Form (HCPs)	At the point of enrolment into the qualitative sub-study

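### AECOPD admissions that a site judges related to BCG are exempt from the SAE form and have no stated route to the Trial Office, which contradicts sections 10.5.2 and 10.6

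*Protocol*

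**What the plan says.** Five parts of Protocol section 10 bear on this.

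- **10.2** excludes exacerbations from adverse event reporting: "Exacerbations of COPD will not be reported as Adverse Events in this study as they are expected in this patient population".
- **10.4.2** covers admission for AECOPD: "Duplication of data collection via SAE forms is therefore not planned". What remains is local recording: "Such events should still be recorded by the trial team in the participant's notes and as a trial outcome".
- **10.4.3** sets the 24-hour rule for "All SAEs not listed in Sections 10.4.1 and 10.4.2", so AECOPD admissions fall outside it.
- **10.5.1 and 10.5.2** describe the Chief Investigator's independent causality review, which the Trial Office requests once an SAE form is completed, and the expectedness assessment of related SAEs. Section 10.5.2 also says that the Chief Investigator reviews every SAE.
- **10.6** states the onward duty: "The Trial Office will report details of all SARs (including SUSARs) to the MHRA", with fatal or life-threatening SUSARs going to the regulator, ethics committee and sponsor's governance team within 7 days.

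Sites do grade causality locally. Section 10.4.1 requires causality and severity of serious events in the participant's notes, and 10.5.1 asks for the same causality categories in the source data for exempt SAEs.

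**The concern.** Exempting an endpoint event from SAE forms is a reasonable way to avoid recording it twice. The difficulty is that this exemption is attached to the type of event and not limited by relatedness. That exacerbations are common in these patients describes their background frequency. It does not settle whether a particular admission, after a live attenuated vaccine given to alter immune response, was caused by that vaccine.

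Under section 10.1 the reporting investigator's judgement alone is enough to make an event an adverse reaction. An AECOPD admission that the site grades as possibly, probably or definitely related is therefore a SAR by the protocol's own definition. If the sponsor never receives that grade, it cannot assess expectedness, cannot recognise a SUSAR and cannot meet the reporting times in 10.6 for that case.

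**Working it through.** No arithmetic is needed to establish the gap. The check is to follow one event through the text: a participant in the BCG arm is admitted with an AECOPD and the site investigator considers it possibly related to the vaccine.

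1. **Is it serious?** Yes. Section 10.1 lists "Results in death Is life-threatening* Requires hospitalisation or prolongation of existing hospitalisation", and hospitalisation alone suffices.
2. **Is it a reaction?** Yes. Under 10.1 the reporting investigator's causal judgement suffices, and Table 4 in 10.5.1 counts a grade of possibly as related. The event is a SAR.
3. **Does an SAE form follow?** No. Section 10.4.2 exempts it, with no condition on relatedness, and 10.4.3 removes 10.4.2 events from the 24-hour route.
4. **Does the Chief Investigator review causality?** Not by any stated path. The trigger in 10.5.1 is a completed SAE form.
5. **Is expectedness assessed?** Section 10.5.2 gives this to the Chief Investigator for related SAEs, but nothing has told the Chief Investigator that this one exists.
6. **Is it reported onward?** Section 10.6 says that every SAR is. The Trial Office has not been told of the causality grade, so it has nothing to act on.

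Steps 3 and 4 cannot both be followed and leave 10.5.2 and 10.6 true.

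**Fatal or life-threatening cases.** Section 10.1 lists death and threat to life as criteria separate from hospitalisation, while the title of 10.4.2 names admission only.

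- A fatal exacerbation without admission is not listed in 10.4.1 or 10.4.2, so on its face 10.4.3 requires a report. Section 10.2 points the other way.
- For a death during an AECOPD admission, the text does not say which rule governs.
- Section 10.5 adds to the uncertainty by sending the reader to 10.4.2 for the SAE form timeline, although 10.4.2 is the section that says no form is planned.

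**Other routes by which the information might arrive.**

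- The adjudication committee (6.7, 18.7) is blinded to allocation, so it cannot judge relation to the vaccine.
- The DMC (10.6, 18.6) may review SAEs and, where appropriate, receives primary and major secondary outcomes, with at least annual meetings. That is comparison of arms, not case-level causality review.
- The exacerbation form (11.2) is due at the event but is completed by the participant, and it is described as covering symptoms and treatment.
- Deaths reach the Trial Office on the status form, due "At the point of change of status, withdrawal or death". No causality assessment is described for it.

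**Timing.** Hospitalisations are collected at 3 and 12 months (9.5 to 9.7). An admission just after the month 3 form, for which no at-event form arrives, is captured at month 12: 12 − 3 = 9 months. This is the worst case for admissions, not the usual delay.

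**The case against.** The strongest reply is that not recording endpoint admissions twice is a deliberate and common choice, and that other data cover most of what is lost. Much of this stands.

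- **Causality is assessed, at the site.** A reader might infer that these events get no causality assessment at all. Sections 10.4.1 and 10.5.1 show otherwise. What is missing is transmission to the Trial Office and review by the Chief Investigator.
- **The reporting system is not disabled.** A reader might infer that SAR and SUSAR reporting cannot work in this trial. It works for every SAE outside 10.4.1 and 10.4.2.
- **The exemption does not plainly cover every fatal case.** Section 10.4.2 is confined to admissions, so for fatal and life-threatening events the defect is ambiguity, not a clear exclusion.
- **Long delay is not the rule.** Deaths are notified on the status form, with submission expected within four weeks (11.2). Admissions may be known early from the at-event form, with a telephone call or record check when treatment data are missing (11.3), and the adjudication committee meets every three months.
- **An excess of severe exacerbations is best seen by comparing arms.** Severe AECOPD falls within the primary outcome and is also the first-listed secondary outcome, so the DMC may already see it.

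None of this gives a site-judged related AECOPD admission a route to the sponsor. The at-event form and the adjudication process carry the fact of an exacerbation; neither is described as carrying the site's causality grade. The contradiction with 10.5.2 and 10.6 remains.

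**Conclusion.** The point holds for a defined class of event: AECOPD admissions in vaccinated participants that the site considers related to BCG. Followed exactly, the protocol keeps the causality grade for these in the source notes, while 10.5.2 and 10.6 promise central review and onward reporting. For fatal or life-threatening AECOPD admissions the text is unclear, and sites could reasonably read it either way.

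The protocol gives no figure from which to count the affected events. It states no expected share of admissions that would be fatal, life-threatening or judged related, and the 38% in section 1.1 combines death with readmission. The total number of AECOPD admissions would be the wrong measure: routine admissions can properly stay exempt, and participants in the control arm cannot have a reaction to a vaccine they did not receive. The conclusion does not depend on a count, since a single related admission is enough to put the sections in conflict.

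It does rest on the protocol text alone. If a safety reporting instruction outside the protocol already requires these cases on an SAE form, the protocol still needs to say so.

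**What to change.** Reconcile sections 10.2, 10.4.2, 10.4.3, 10.5.2 and 10.6:

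- In 10.4.2, keep the exemption for ordinary AECOPD admissions. Add that an AECOPD event that is fatal, life-threatening, or graded possibly, probably or definitely related to BCG is reported on the SAE form under 10.4.3 and reviewed under 10.5.1 and 10.5.2.
- In 10.2, make the statement about exacerbations subject to that exception.
- In 10.5.2, say that the Chief Investigator reviews all reported SAEs, so that it agrees with the exemption. With the exception in place, the commitment in 10.6 can stand.
- In 10.5, point the SAE form timeline to 10.4.3.
- In 10.6 or 18.6, state that AECOPD admissions and all deaths are tabulated by arm in DMC reports.

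The cost is a protocol amendment in wording and a small number of extra SAE forms. Routine admissions stay exempt, and the DMC table uses data already collected. The sample size, outcomes and analysis do not change.
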